***The ECG should be completed prior to study drug escalation on Treatment Day 1 at 12 Hours (Dose Levels 2 and 3).**

- Document urine volume, take a sample from 0-12h urine volume, and begin 12-24h collection interval; and
- AE review and reporting.

Treatment Day 1 at 18 hrs

- Ammonia collection;
- Continuous monitoring and collection of mean arterial pressure;
- Continuous monitoring and collection of intracranial pressure (ICP) (if applicable); and
- AE review and reporting.

End of Treatment Day 1 at 24 hrs / Day 2 at 0 h

- OCR-002 Infusion for Level 3 dosing only (the infusion rate will be increased to 0.416 g/hour for the remainder of the study), provided previous dose levels are well tolerated with no noteworthy side effects and the patient's Cohort dosing level assignment.
Dose Level 4 - continue on maintenance infusion of OCR-002;
- Collection of concomitant medications (if applicable);
- Collection of blood for hematology, coagulation, clinical chemistry, ammonia and PK;
- Urinalysis*;
*Urinalysis: dipstick plus microscopic evaluation of sediment, if clinically indicated.
- Vital signs and abbreviated physical exam;
- Neurological battery, including
 - Glasgow Coma Scale;
 - West-Haven Scale; and
 - O-Log Scale;
- 12-lead ECG**;

****The ECG should be completed prior to study drug escalation on Treatment Day 2 at 0 Hours (Dose Levels 2 and 3).**

- Document urine volume, take a sample from 12-24h urine volume, and start 24-36h collection;
- Continuous monitoring and collection of mean arterial pressure;
- Continuous monitoring and collection of intracranial pressure (ICP) (if applicable); and
- AE review and reporting.

Treatment Day 2 at 6 hrs

- Ammonia collection;
- Continuous monitoring and collection of mean arterial pressure;
- Continuous monitoring and collection of intracranial pressure (ICP) (if applicable); and
- AE review and reporting.

Treatment Day 2 at 12 hrs

- Continue on maintenance infusion of OCR-002;
- Collection of concomitant medications (if applicable);
- Collection of blood for hematology, coagulation, clinical chemistry, ammonia and PK;
- Vital signs and abbreviated physical exam;
- Neurological battery, including:
 - Glasgow Coma Scale;
 - West-Haven Scale; and
 - O-Log Scale;
- 12-lead ECG;
- Document urine volume, take a sample from 24-36h urine volume, and start 36-48h urine collection;
- Continuous monitoring and collection of mean arterial pressure;
- Continuous monitoring and collection of intracranial pressure (ICP) (if applicable); and
- AE review and reporting.

Treatment Day 2 at 18 hrs

- Ammonia collection;
- Continuous monitoring and collection of mean arterial pressure;
- Continuous monitoring and collection of intracranial pressure (ICP) (if applicable); and
- AE review and reporting.

End of Treatment Day 2 at 24 hrs/ Day 3 at 0 h

- Continue on maintenance infusion of OCR-002;
- Collection of concomitant medications (if applicable);
- Collection of blood for hematology, coagulation, clinical chemistry, ammonia and PK;

- Urinalysis*;
*Urinalysis: dipstick plus microscopic evaluation of sediment, if clinically indicated.
- Vital signs and abbreviated physical exam;
- Neurological battery, including:
 - Glasgow Coma Scale;
 - West-Haven Scale; and
 - O-Log Scale;
- 12-lead ECG;
- Document urine volume, take a sample from 36-48h urine volume, and start 48-72h urine collection;
- Continuous monitoring and collection of mean arterial pressure;
- Continuous monitoring and collection of intracranial pressure (ICP) (if applicable); and
- AE review and reporting.

Treatment Day 3 at 12 hrs

- Ammonia collection;
- Collection of concomitant medications (if applicable);
- Neurological battery, including:
 - Glasgow Coma Scale;
 - West-Haven Scale; and
 - O-Log Scale;
- Continuous monitoring and collection of mean arterial pressure;
- Continuous monitoring and collection of intracranial pressure (ICP) (if applicable); and
- AE review and reporting.

End of Treatment Day 3 at 72 Hours / Day 4 at 0 h

- Continue on maintenance infusion of OCR-002;
- Collection of concomitant medications (if applicable);
- Collection of blood for hematology, coagulation, clinical chemistry, ammonia and PK;
- Urinalysis*;
*Urinalysis: dipstick plus microscopic evaluation of sediment, if clinically indicated.
- Vital signs and abbreviated physical exam;
- Neurological battery, including:
 - Glasgow Coma Scale;
 - West-Haven Scale; and
 - O-Log Scale;
- 12-lead ECG;

- Document urine volume, take a sample from 48-72h urine volume, and start 72-96h urine collection;
- Continuous monitoring and collection of mean arterial pressure;
- Continuous monitoring and collection of intracranial pressure (ICP) (if applicable); and
- AE review and reporting.

End of Treatment Day 4 at 96 Hours / Day 5 at 0 h

- Continue on maintenance infusion of OCR-002;
- Collection of concomitant medications (if applicable);
- Collection of blood for hematology, coagulation, clinical chemistry, ammonia and PK;
- Urinalysis*;
 - * Urinalysis: dipstick plus microscopic evaluation of sediment, if clinically indicated.
- Vital signs and abbreviated physical exam;
- Neurological battery, including:
 - Glasgow Coma Scale;
 - West-Haven Scale; and
 - O-Log Scale;
- 12-lead ECG;
- Document urine volume, take a sample from 72-96h urine volume, and start ~~next 24-96~~-120h urine collection;
- Continuous monitoring and collection of mean arterial pressure;
- Continuous monitoring and collection of intracranial pressure (ICP) (if applicable); and
- AE review and reporting.

Completion of the Last Infusion (at time infusion is stopped)

The following assessments should be administered on all patients who received an infusion of the study drug, including those patients who received the full course of study drug treatment and those patients who do not complete the entire course of study drug treatment.

- Collection of concomitant medications (if applicable);
- Collection of blood for hematology, coagulation, clinical chemistry, ammonia and PK;
- Urinalysis*;
 - * Urinalysis: dipstick plus microscopic evaluation of sediment, if clinically indicated.
- Vital signs and abbreviated physical exam;
- Neurological battery, including:
 - Glasgow Coma Scale;
 - West-Haven Scale; and
 - O-Log Scale;
- 12-lead ECG;

- Document urine volume, take a sample from 96-120h urine volume, and start 120-144h urine collection;
- Continuous monitoring and collection of mean arterial pressure;
- Continuous monitoring and collection of intracranial pressure (ICP) (if applicable); and
- AE review and reporting.

24 hours Following Completion of the Last Infusion

The following assessments should be administered on all patients who received an infusion of the study drug, including those patients who received the full course of study drug treatment and those patients who do not complete the entire course of study drug treatment.

- Collection of concomitant medications (if applicable);
- Collection of blood for hematology, coagulation, clinical chemistry, ammonia and PK;
- Urinalysis*;
* Urinalysis: dipstick plus microscopic evaluation of sediment, if clinically indicated.
- Vital signs and abbreviated physical exam;
- Neurological battery, including:
 - Glasgow Coma Scale;
 - West-Haven Scale; and
 - O-Log Scale;
- 12-lead ECG;
- Document urine volume and take a sample from 120-144h urine volume; end urine collection;
- Continuous monitoring and collection of mean arterial pressure;
- Continuous monitoring and collection of intracranial pressure (ICP) (if applicable); and
- AE review and reporting.

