Study Design	
This is a Phase 2a, multi-center, open-label study, conducted in two cohorts of patients diagnosed with acute liver failure/severe acute liver injury (ALF/ALI) who meet inclusion/exclusion criteria. Cohort 1 is defined as patients with ALF/ALI with minimal renal dysfunction at the time of enrollment (defined as a serum creatinine ≤ 1.5 mg/dL and mean arterial pressure of >65 mm Hg). Cohort 2 is defined as patients with ALF/ALI with compromised renal function (defined as a serum creatinine >1.5 mg/dL and <10 mg/dL with mean arterial pressure of >65 mm Hg).
 
Informed consent will be obtained from the patient and/or patient's legally authorized representative (LAR) or family member as defined in 21CFR50.3(m). All patients will receive medical care for acute liver failure/severe acute liver injury according to the institution's standards of care. Standard of care may include, but is not limited to, administration of N-acetylcysteine and consideration for orthotopic liver transplantation.
 
Up to 36 evaluable patients will be enrolled. An evaluable patient is one who has received an infusion of OCR-002 for at least 72 hours. It is expected that not every enrolled patient will be treated for at least 72 hours due to transplant, death or early hospital discharge. Due to this, we anticipate 25% of the enrolled population will fail to reach evaluable status. Therefore, we plan to enroll up to 50 patients in order

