4 OBJECTIVES AND ENDPOINTS

4.1 *Objectives*

4.1.1 **Primary Objective**

To evaluate the safety and tolerability of OCR-002 in patients with acute liver failure/severe acute liver injury.

Hypothesis: Treatment with OCR-002 is safe and tolerable in patients with acute liver failure/acute liver injury.

4.1.2 **Secondary Objectives**

To evaluate the steady state pharmacokinetic and pharmacodynamic profile of OCR-002 in patients with impaired and minimal renal dysfunction using urinary PAGN as a surrogate marker.

Hypothesis: A dose of 10-20g/24h (0.42-.83g/h) will achieve steady state plasma concentrations within 6-12h with little additional accumulation in the ALI/ALF setting.

To evaluate the effect of OCR-002 on ammonia levels in patients with acute liver failure/severe acute liver injury.

Hypothesis: Treatment with OCR-002 will reduce ammonia levels in patients with ALI/ALF.

To evaluate the effect of OCR-002 on neurological function in patients with acute liver failure/severe acute liver injury.

Hypothesis: Treatment with OCR-002 will improve neurological function in patients with acute liver failure/severe acute liver injury.

4.2 *Endpoints*

4.2.1 **Safety Endpoints**

Safety assessments will include: abbreviated physical examinations, vital signs (blood pressure, pulse rate, respiration rate, and body temperature), clinical laboratory tests (hematology and serum chemistry), 12-lead ECGs, and reported and observed adverse events.

4.2.2 **Exploratory Efficacy Endpoints**

- Ammonia concentrations.
- Neurological assessment will be measured by the Glasgow Coma Scale, the West Haven Criteria, and the Orientation log (O-log) (34).

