11.7.5 Physical Exams

Physical examination findings at baseline will be listed. Clinically significant changes will be recorded as AEs. Symptoms of interest previously reported with OCR-002 will be recorded daily, including dizziness, headache, nausea, vomiting; daily monitoring of heart rate in relation to infusion initiation will also be recorded.

11.7.6 Plasma Ornithine, Phenylacetate, Phenylacetylglutamine and Glutamine Concentrations and Pharmacokinetic Parameters

Individual and mean plasma ornithine, phenylacetate, and PAGN concentrations at each sampling time point will be presented by listings and descriptive summary statistics. Plasma ornithine, phenylacetate, and PAGN concentration versus time profiles will be plotted.

In addition, individual and mean cumulative urinary PAGN output will be listed with descriptive statistics in tabular format.

Pharmacokinetic parameters will be calculated from plasma ornithine, phenylacetate, and PAGN. Individual plasma ornithine, phenylacetate, and PAGN parameters will be listed for each patient and summary statistics will be provided.

The following PK parameters will be calculated or derived from the data:

- Maximum observed plasma concentration (C_{max});
- Concentration at steady state (C_{ss});
- Clearance at steady state (CL_{ss}); and
- Interval estimates of exposure (e.g. AUC_{0-24h}) over multiple dosing days.

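### Urine intervals keep full-course labels for early stoppers, and mean cumulative urinary PAGN by renal cohort alone is confounded by dose level, infusion length and dialysis

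*Combined protocol and SAP*

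**What the plan says.** Section 4.1.2 sets a secondary objective on the steady-state PK and PD profile "in patients with impaired and minimal renal dysfunction using urinary PAGN as a surrogate marker".

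Section 8.3 collects urine over 0-12, 12-24, 24-36, 36-48, 48-72, 72-96 and 96-120 h. The next visit heading begins "Completion of the Last Infusion (at time infusion is stopped". The visit applies to everyone infused, including "those patients who do not complete the entire course of study drug treatment". Its urine step reads "Document urine volume, take a sample from 96-120h urine volume, and start 120-144h urine collection". The visit 24 hours later has the same scope and reads "Document urine volume and take a sample from 120-144h urine volume; end urine collection". No other interval is given for a patient who stops before 120 h.

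Section 11.7.6 states that "individual and mean cumulative urinary PAGN output will be listed with descriptive statistics in tabular format". It gives no end time for the accumulation and no adjustment for dose, collection time or dialysis. Sections 11.2 and 11.6 summarise overall and by cohort and do not name dose level. The closing memorandum confirms that there is no separate SAP, so Section 11 is the whole plan.

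**The concern.** There are two separate problems.

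**Labels.** The visit is tied to the actual stop, but its urine is named as if every infusion ran 120 h. Early stopping is expected: the Synopsis says "we anticipate 25% of the enrolled population will fail to reach evaluable status", and an evaluable patient may stop anywhere between 72 and 120 h.

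**Summary.** Amount excreted depends on amount infused. A cohort mean pooled over four dose levels and unequal durations does not show what fraction of phenylacetate is converted and excreted. A difference between renal cohorts could come from dose mix, infusion length or dialysis. A total that runs through titration, maintenance and washout is also a poor measure for a steady-state objective; excretion rates per interval suit it better.

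**Working it through.** **Plan's own figures.** Rate × 24 h, with rates from the Synopsis (Treatment): 0.139 × 24 = 3.34 g (stated 3.33); 0.277 × 24 = 6.65 g (6.65); 0.416 × 24 = 9.98 g (10); 0.83 × 24 = 19.9 g (20). All agree to within 0.4%.

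**Cumulative planned dose** = sum of rate × hours over the titration steps. It is taken at 72 h, because "An evaluable patient is one who has received an infusion of OCR-002 for at least 72 hours", and at the 120 h maximum. Level 4 uses 20/24 g/h.

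| Level | To 72 h | To 120 h | Ratio |
|---|---|---|---|
| 1 | 0.139×72 = 10.0 g | 0.139×120 = 16.7 g | 1.67 |
| 2 | 0.139×12 + 0.277×60 = 18.3 g | 0.139×12 + 0.277×108 = 31.6 g | 1.73 |
| 3 | 0.139×12 + 0.277×12 + 0.416×48 = 25.0 g | 0.139×12 + 0.277×12 + 0.416×96 = 44.9 g | 1.80 |
| 4 | 60.0 g | 100.0 g | 1.67 |

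- Extreme evaluable pair: 100 / 10.0 = 10-fold.
- Dose level alone, at equal 72 h: 60 / 10.0 = 6.0-fold.
- In molar terms (268.31 g/mol, 1:1 salt, Section 3.2.1): 10.0 g is 37 mmol and 100 g is 373 mmol of phenylacetate. If each mole yields at most one mole of PAGN (an assumption), these are ceilings on output.

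**Labels.** A patient who stops at 80 h closes a collection begun at 72 h. It is 8 h long but carries a 24 h label, so a rate computed from the label is 8/24, one third of the true rate. For a stop at 84 h it is 12/24, one half. The post-infusion collection (80-104 h) has the right length but is displaced by 120 − 80 = 40 h. The sum of volume × concentration over all collections does not change.

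**Dose mix and the cohort mean (illustration, splits assumed).** Suppose all patients are treated for 120 h, Cohort 1 has 3/3/6/6 patients at Levels 1-4, and Cohort 2 stops at 3/3/3 over Levels 1-3.

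- Cohort 1 mean dose: (3×16.68 + 3×31.58 + 6×44.93 + 6×100)/18 = 56.4 g.
- Cohort 2 mean dose: (16.68 + 31.58 + 44.93)/3 = 31.1 g.

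With identical fractional excretion, mean PAGN would differ 56.4/31.1 = 1.8-fold. If both cohorts fill the same levels equally, this component disappears.

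**How much of the spread is dose and duration?** Assume 3/3/6/6 in a cohort, durations uniform over 72-120 h, and an excreted fraction independent of dose. Then SD(ln dose) = 0.651 and the variance is 0.424. The share of log-output variance is 0.424 / [0.424 + ln(1 + CV²)], where CV is the between-patient CV of the excreted fraction.

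| CV | 30% | 50% | 75% | 100% | 200% |
|---|---|---|---|---|---|
| Share | 83% | 66% | 49% | 38% | 21% |

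The share is one half at a CV of about 73%. The documents do not give this CV.

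**The case against.** Several points on the other side stand.

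- A reader might infer that the surrogate mostly reflects dose and infusion length. The documents do not support this. It depends on the unstated CV above, and in Cohort 2 creatinine up to 10 mg/dL and dialysis could matter more.
- A reader might also infer that the labels corrupt the cumulative total. They do not; only interval rates and time-indexed values are at risk.
- It is not known that sites would file the urine under the wrong hours. The CRFs and Manual of Operations are not in the documents, and the labels may be nominal. Section 7.5 records infusion start, stop and total volume, so much could be corrected at analysis.
- Section 11.7.6 fixes no end time. Accumulated to 72 h, output is already comparable for duration in every evaluable patient, because those intervals are correctly labelled. The 6.0-fold spread from dose level remains, and the ITT sensitivity analysis adds patients below 72 h.
- Section 5.1 plans about 18 patients per cohort, and both cohorts pass through the same four levels, which tends to balance dose mix. However, Cohort 2 reaches Levels 3 and 4 only after further SRC review, so balance is not assured.
- The study is descriptive and unpowered. Individual listings, Css, CLss and interval AUC are also planned. These reduce the consequence but do not repair the urinary summary, which is the named surrogate.

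**Conclusion.** The point holds in two parts. First, the last two urine intervals are mislabelled for anyone who stops before 120 h. Interval or time-indexed PAGN would be wrong if the labels were used, while the final total is unaffected. Second, mean cumulative output by renal cohort, with no dose level and no normalisation, is confounded by dose level (6.0-fold at equal duration) and infusion length (1.67- to 1.80-fold within a level), 10-fold between the extremes. These figures assume planned rates without down-titration. The bias in a cohort comparison depends on the dose mix actually enrolled and may be small if the cohorts match.

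Dialysis adds a further confounder. Section 3.3.1 notes that PAGN can be dialysed, and Section 5.1 has CVVHD considered in Cohort 2 at creatinine of 2.0 or more.

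This is a gap in the written plan for a secondary objective. It is not shown to be a loss of data, and it should be corrected.

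**What to change.** - **Section 8.3:** define the last two urine intervals by actual start and stop times, and flag each as on-infusion or post-infusion.
- **Section 11.7.6:** summarise urinary PAGN by dose level within cohort, as mmol/h per interval and as molar per cent of phenylacetate actually infused to that time. Use a common cut-off, for example 0-72 h, for evaluable patients.
- **Dialysis:** flag or separate patients on dialysis or CVVH, because urinary recovery understates PAGN formation in them. Normalising by dose does not solve this.
- **Raw output:** keep cumulative PAGN as a descriptive summary by dose level, since amount excreted is a stated purpose of the collection.

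The cost is modest: revised text, and CRF fields for urine start and stop times if these are not already captured. Dose infused to a given time also needs the times of rate changes, which Section 7.5 does not name. The downside is a few more tables and small cells by dose level.

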8.4 Follow Up or Early Termination

A safety follow-up visit will be performed approximately 30 days from Treatment Day 1-T0 (start of infusion) for all patients who completed the study drug infusion period or who discontinued the study drug infusions but remain in the study.

- Collection of blood for hematology, coagulation, clinical chemistry, ammonia;
- Vital signs and abbreviated physical exam;
- Neurological battery, including:
 - Glasgow Coma Scale;
 - West-Haven Scale; and
 - O-Log Scale;
- Review and reporting of Serious Adverse Events (SAEs).*

* Non-serious adverse events (AEs) and Serious Adverse Events (SAEs) are collected from Treatment Day 1 at T0 through 24 hours Following Completion of the Last

Infusion. After the 24 hours Following the Completion of the Last Infusion time point, only SAEs are collected through the Day 30 post treatment period.

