Study Design Continued	
to obtain 36 evaluable patients. Dosing with OCR-002 may be initiated immediately after obtaining signed informed consent; or, up to 32 h after obtaining consent should the time be necessary to complete any pre-study drug initiation requirements and/or to provide a time frame for study drug administration.
 
Baseline is immediately prior to the start of the initial infusion. At Treatment Day 1 - Time “0” (T0) and after baseline measurements, patients enrolled at Dose Levels 1 through 3 will receive an initial infusion rate of OCR-002. Dose will be escalated to a maximum dose of 10g/24h infusion as indicated herein. Patients receiving Dose Level 4 will receive the full 20 gm/24 hour dose level from initiation of infusion for a maximum time of 120 hours with no further dose escalation, provided the dose level is well tolerated with no noteworthy side effects. Titration of dose will depend on evidence of safety and tolerability (refer to Treatment section below).
 
Patients may have an IV catheter inserted as a safer and easier method for obtaining repeated blood sampling and a separate IV for the infusion. Blood samples for measurement of plasma ornithine, phenylacetate and PAGN concentrations will be collected at multiple time-points during the infusion period, at the Completion of the Last Infusion and up to 24 hours Following the Completion of the Last Infusion. Urine will be collected at specific intervals to determine the amount of PAGN excreted.
 
Patients will be assessed for safety and tolerability of OCR-002 as well as pharmacokinetic and pharmacodynamic variables during the infusion period, at the Completion of the Last Infusion and 24 hours Following the Completion of the Last Infusion. Data on clinical outcomes will also be collected during the study period.
 
Safety data will be reviewed by a Safety Review Committee (SRC) operating under an approved charter and made up of three ALFSG clinicians who are independent of the participating clinical sites and a clinical pharmacologist with experience in PK and clinical trials. Throughout the trial, the SRC will review all safety data at regular intervals, and the FDA will receive annual IND reports.
 
Supportive Care
 
Inotropic support may be used to maintain mean arterial pressure above 65 mm Hg in patients who are hypotensive either before or after enrollment. Dialysis or continuous veno-venous hemofiltration (CVVH), endotracheal intubation and mechanical ventilation will be considered as indicated. Cerebral edema will be managed post-enrollment with mannitol or hypertonic saline per local institutional practices. Antibiotic therapy may be initiated and modified as required. In patients who have intracranial pressure (ICP) monitors placed, ICP, cerebral perfusion pressure and mean arterial pressure will be recorded continuously and reported hourly.

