Exploratory Efficacy Evaluations	
Ammonia concentrations will be collected during the infusion period, at the Completion of the Last Infusion, 24 hours Following the Completion of the Last Infusion and at the Day 30 post treatment period. Neurological assessments measured by the Glasgow Coma Scale and the West Haven Criteria will be done every 12 or 24 hours during the entire infusion period. Orientation log (O- log) assessment will also be undertaken in all patients at these time points.

Concomitant Medications and Therapy	
All patients will receive or have received, intravenous N-acetylcysteine (NAC) for acetaminophen toxicity.
 
Third generation cephalosporins, hypertonic saline and/or mannitol are permitted.
 
The use of hypothermia therapy is prohibited during the study.

Safety Analysis	
All adverse events will be summarized by body system, preferred MedDRA term and cohort. Data listings and summaries of severity, relation to treatment and expectedness will be provided by cohort.

Statistical Considerations	
This study is not powered to determine statistical significance. Descriptive statistics will be used to evaluate safety, exploratory efficacy data, PK and PD.

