3 INTRODUCTION AND BACKGROUND

3.1 *Introduction*

Acute liver failure (ALF) is a rare disorder affecting an estimated 2000 patients annually in the United States (US). Hepatotoxicity related to the use of acetaminophen is the most common etiology of ALF in the US (1).

Acute liver failure is the result of massive damage to previously normal liver parenchyma with resultant loss of liver function. As the hepatocyte function is lost, the liver loses its ability to synthesize proteins and extract circulating toxins. The two cardinal signs of ALF, coagulopathy and encephalopathy, represent the loss of the ability to synthesize clotting factors and to remove ammonia, respectively.

Acute liver failure often affects young people and carries a very high mortality. Only 45% of patients with ALF will spontaneously recover. Of the remaining 55%, 30% will die and 25% will undergo an emergency liver transplantation. Emergency liver transplantation in this setting has a 90% 1-month survival rate and a 70% 1-year survival rate. Mortality in ALF can be due to a variety of factors, including sepsis and multi-organ system failure, but cerebral edema due to increased ammonia resulting in intracranial hypertension and brainstem herniation is one of the most common causes of death, accounting for 30% of the mortality in this population (2).

There is strong experimental and clinical rationale for the use of ammonia-lowering therapies in ALF. Ammonia is normally produced in the gut and transformed by the liver into urea. As the liver fails, ammonia increases in the systemic circulation and enters into the brain. The result of a rapid rise in ammonia in the cerebral circulation is hepatic encephalopathy (HE), a reversible neuropsychiatric condition that ranges in severity from mild impairment in attention, to delirium, coma and death. A particular concern regarding HE in ALF is that ammonia level increases tend to be very rapid. This rapid rise in ammonia does not provide sufficient time for brain cells to compensate, with the end result being astrocyte swelling with increased intracranial pressure (ICP) and ultimately, death due to brain herniation. An arterial ammonia level above 150 μ M has been shown to correlate with a poor prognosis, and is almost universally indicative of increased intracranial pressure (3).

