11.3 Sample Size Determination

This is an exploratory pilot study and no formal sample size calculation was performed for this study.

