11.6 Statistical Analyses

Tables and listings will be produced using SAS v9.2 or higher (SAS, Cary, NC). Data summaries by cohort group will be presented. For continuous variables, data will be summarized with the number of patients, mean, standard deviation, median, and minimum and maximum overall and by cohort. For categorical variables, data will be tabulated in frequency tables to display the number and proportion of patients for each category overall and by cohort. Baseline assessments for each outcome variable will be defined as the last measurement obtained before treatment initiation. Each point estimate will be presented with 2-sided 95% confidence intervals and all statistical tests will use a two-sided 5% significance level.

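### Section 11 has no rule for ammonia or neurological values after transplant or death, so apparent improvement is expected at Day 30, and possible earlier, even if the drug is inactive

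*Combined protocol and SAP*

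**What the plan says.** - **Timing.** The synopsis lists ammonia as exploratory efficacy data during infusion, when infusion ends, and "24 hours Following the Completion of the Last Infusion and at the Day 30 post treatment period". Section 8.3 schedules ammonia and all three neurological scales at infusion stop and 24 hours later for every infused patient, including those who stop early. Section 8.4 repeats both at Day 30: "A safety follow-up visit will be performed approximately 30 days from Treatment Day 1-T0 (start of infusion").
- **Transplant.** Section 6.3.4 lists it as a reason to stop treatment. Section 6.3.5 then follows patients who stop early for the 30 days unless consent is withdrawn, and Section 8.4 includes them in the Day 30 visit if they remain in the study.
- **Analysis.** For continuous variables, Section 11.6 says "data will be summarized with the number of patients, mean, standard deviation, median, and minimum and maximum overall and by cohort", and it attaches 95% intervals to point estimates. Section 11 has no subsection for ammonia or neurological scores and no rule for transplant, death or missing values. The memorandum at the end confirms that there is no separate SAP.
- **Analysis sets.** Section 11.4 makes the per-protocol set (at least 72 hours of drug) primary for all outcomes, with ITT as sensitivity analysis.
- **Outcomes.** The synopsis says "Data on clinical outcomes will also be collected during the study period", but Section 11 plans no table of death or transplant beyond what the adverse event tabulations show.

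**The concern.** After a transplant, ammonia and mental state reflect the new liver and no longer the study drug acting on a failing one. A patient who dies has no later value, so later summaries describe survivors. Both mechanisms push the observed data towards improvement. Section 4.1.2 states directional hypotheses for ammonia and for neurological function, and the only evidence on them will be these summaries. Without a rule, anyone applying 11.6 literally would pool post-transplant and native-liver values and leave out the dead. A favourable change, with a confidence interval around it, could then be read as drug effect. Reporting the number of patients observed would show the shrinkage but not its causes.

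**Working it through.** **The plan's own figure.** The plan gives no effect size, SD or power for these endpoints; Section 11.3 says "no formal sample size calculation was performed for this study". The one related figure is enrolment. The synopsis says "we anticipate 25% of the enrolled population will fail to reach evaluable status", naming transplant, death and early discharge as causes, and "Therefore, we plan to enroll up to 50 patients in order" to reach 36. The check is 36/(1 − 0.25) = 48, consistent with up to 50. The plan thus expects these events but has no analysis rule for them.

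**Inputs (Section 3.1, acute liver failure).** Spontaneous recovery is 45%; of the remaining 55%, "30% will die and 25% will undergo an emergency liver transplantation". Since 30 + 25 = 55, these are shares of all patients. One-month patient survival after transplant is 90%.

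**Day 30 make-up with an inactive drug.** Assumptions: all treated patients, all with acute liver failure, deaths and transplants before Day 30, and the one-month figure standing in for survival to Day 30.

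- Transplanted and alive: 0.25 × 0.90 = 0.225
- Alive: 0.45 + 0.225 = 0.675
- Transplant recipients among the living: 0.225/0.675 = 1/3
- Dead, no value: 1 − 0.675 = 0.325

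| Treated | Alive | Transplanted, alive | Spontaneous recovery | Dead |
|---|---|---|---|---|
| 36 | 24.3 | 8.1 | 16.2 | 11.7 |
| 50 | 33.75 | 11.25 | 22.5 | 16.25 |

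On these figures, everyone measured at Day 30 has either recovered or received a new liver.

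**Sensitivity to case mix.** The ratio of acute liver failure to acute liver injury is not given. If half had acute liver injury, with 10% mortality (Section 9.1.2) and no transplants (assumed), then alive = 0.5 × 0.675 + 0.5 × 0.90 = 0.7875, and the transplant share is 0.1125/0.7875 = 14%.

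**Ammonia illustration.** The documents give no ammonia levels by outcome, so all levels here are assumed: baseline means in µmol/L for recover/transplant/die, and 30 to 50 in survivors at Day 30. The drug does nothing.

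| Assumed baseline | Mean, all | Mean, survivors | Shift from losing the dead | Paired change, all survivors | Paired change, spontaneous survivors |
|---|---|---|---|---|---|
| 100/100/100 | 100.0 | 100.0 | 0.0 | −70 to −50 | −70 to −50 |
| 90/110/130 | 107.0 | 96.7 | −10.3 | −66.7 to −46.7 | −60 to −40 |
| 90/130/170 | 124.0 | 103.3 | −20.7 | −73.3 to −53.3 | −60 to −40 |

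For example, in row 2: 0.45 × 90 + 0.25 × 110 + 0.30 × 130 = 107.0, and (0.45 × 90 + 0.225 × 110)/0.675 = 96.7.

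With 24 survivors, a mean change of −40 and an assumed SD of 40 to 60, the standard error is 8.2 to 12.2. By normal approximation, the 95% interval excludes zero with probability 0.998 to 0.90.

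**During infusion.** If 25% to 75% of those who die or are transplanted are unobserved by 120 hours and nobody's ammonia changes, the mean moves by 0 to about −20 under the same baselines (for example 124.0 to 104.5).

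**The case against.** Much of the case for the plan stands, and it limits the point.

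- **By-visit averaging is inferred.** A reader might take it that the plan prescribes means at each visit and a Day 30 change for these endpoints. It does not. Tabulation by time point is written for vital signs and PK, and change from baseline for laboratory tests, vital signs and ECG. The gap is that nothing is specified; pooling is the natural default under 11.6.
- **Day 30 is called a safety visit**, and the synopsis places the neurological efficacy assessments within the infusion period. But it names Day 30 for ammonia under exploratory efficacy, and the values at infusion stop and 24 hours later are exposed as well.
- **The one-third share is not the primary summary.** The per-protocol set removes deaths and transplants before 72 hours. It adds its own survivor selection and keeps later transplants, and the ITT analysis readmits the early ones without a rule.
- **The share may be too high here.** Section 3.3.1 says many acetaminophen patients cannot be listed for transplant. The 90% is patient survival counted from transplant, not graft survival or survival from the start of infusion.
- **Transplant and survivorship are not the only causes.** A reader might infer that they alone would make both hypotheses look supported. The documents do not show this: there is no control arm, 45% recover spontaneously, and entry requires ammonia of at least 60 µmol/L, so some fall is likely anyway. In the illustration, spontaneous survivors alone still show −40 to −70. Acute liver injury patients enter without encephalopathy and have little room to improve neurologically.
- **The study is exploratory and unpowered.** That lowers the stakes but does not correct a misleading estimate reported with an interval.

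**Conclusion.** The concern holds in a limited form. Section 11 does not say what happens to ammonia and neurological values after transplant or death, and the follow-up rules keep transplanted survivors in the data 24 hours after infusion and at Day 30. Summaries of available values would mix post-transplant and survivor-only data. An apparent improvement at Day 30 is then expected with an inactive drug. Earlier it is possible, depending on when events occur and how ammonia differs by outcome; worsening patients still under observation could offset it.

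The size, 67.5% alive with one third of them transplant recipients, rests on the protocol's acute liver failure figures for all treated patients with events before Day 30. It is 14% in the half-and-half mix above and cannot be computed for the per-protocol set. The ammonia shifts rest on assumed levels and show direction only. The documents do not support saying that improvement is certain at every time point.

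**What to change.** Amend Section 11.6 as follows.

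1. Base the main ammonia and neurological summaries on a stated on-treatment window, using pre-transplant values only. List post-transplant values separately.
2. In the ordinal neurological summary, count death and transplant as the worst categories instead of dropping these patients, and state their order. Show the two counts separately, because transplant also depends on who can be listed.
3. Beside each time point, for both PP and ITT, give the numbers on infusion, off infusion alive with native liver, transplanted, dead, and discharged or missing.
4. Report Day 30 ammonia and neurological values descriptively by status (native liver or transplanted). State that change from baseline cannot be attributed to the drug, because there is no control arm and spontaneous recovery is common.

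Restricting Day 30 means to native-liver patients would not be enough: on the protocol's figures, that leaves only the 45% who recovered spontaneously.

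The cost is SAP wording and one extra table, using data that the plan already says it collects. The price is fewer values in the later summaries. No treatment or follow-up procedure changes.
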